2. INTRODUCTION

The formation of wrinkles at the corners of the eyes, which are referred to as crow's feet lines or LCLs, are one of the primary signs of aging that can negatively impact the assessment of a person's age. These dynamic lines appear during facial muscle contractions, like smiling, and over time can become permanent or static, meaning that they are still visible when without muscle contraction (Kane, 2015).

Minimally-invasive injectable treatments have become the most common aesthetic procedure worldwide (Baumann, 2016) with an increase in frequency over the last decade since the first approval of botulinum neurotoxin Type A (OnabotulinumtoxinA; BOTOX[®] Cosmetic; [package insert]. Allergan, Inc., 2017). This is largely the result of an exceptional safety profile, as well as the ability of botulinum neurotoxin Type A to rejuvenate and enhance the facial area when compared with more invasive cosmetic procedures.

Botulinum neurotoxin is produced by *Clostridium botulinum*, which is a gram-positive, spore-forming, anaerobic bacterium (Carruthers, 2015a). There are 7 distinct types (A-G), only types A and B have established clinical uses due to a longer duration of action compared to the other types (De Boulle, 2007). Botulinum neurotoxin Type A blocks acetylcholine release into the neuromuscular junction, which prevents muscle contractions in the injected area. The onset of muscle weakening typically begins within 48 hours after treatment and usually lasts between 4 and 5 months, although some patients have reported shorter or longer durations (Nestor, 2017; Carruthers, 2015; De Boulle, 2007).

The presence of facial lines at rest result from a combination of factors, including repeated facial muscle contractions, structural skin remodeling that occurs with aging, and damage from excessive sun exposure (Carruthers, 2016). Carruthers, et.al., identified 4 distinct patterns for lateral canthal lines: full-fan, lower-fan, central-fan, and upper-fan. The description of these lines emphasizes the orientation of the lines in the lateral canthal area and nearby facial regions. As the dynamic patterns for LCL are further elucidated, it has become possible for experienced practitioners to customize treatment of the lateral canthal region to match the pattern of a patient's lateral canthal lines.

The efficacy and safety of onabotulinumtoxinA for the treatment of LCL has been evaluated in a large-scale clinical development program consisting of 3 phase 3 studies (Carruthers, 2015b). Study 1 evaluated onabotulinumtoxinA for the treatment of LCL alone. A total of 445 subjects with moderate to severe LCL were randomized to receive either onabotulinumtoxinA 24 U (N=222) or placebo (N=223) (Baumann, 2016). At baseline, 60.5% of subjects had severe LCL. The primary efficacy endpoint was investigator-assessed response of LCL at maximum smile on the Facial Wrinkle Severity (FWS) scale at Day 30. Responder rates were significantly higher in the onabotulinumtoxinA-treated groups when compared with placebo. Composite investigator- and subject-assessed improvement of at least 2 grades from baseline scores on the FWS at Day 30 were higher for the onabotulinumtoxinA-treated group (26.1%) when compared with placebo (1.3%) (Carruthers, 2015b).

Study 2 was a 7-month, double-blind, randomized, placebo-controlled, parallel-group study with 2 treatment cycles of onabotulinumtoxinA or placebo. A total of 917 subjects were enrolled:

305 subjects received onabotulinumtoxinA 44U (24 U to LCL area and 20 U to GL area), 306 subjects received onabotulinumtoxinA 24 U (12 U to LCL Area and 0 U to GL area), and 306 subjects received placebo (Moers-Carpi, 2015). The primary efficacy outcome was based on investigator and subject assessments of LCL severity at maximum smile at Day 30 using an FWS. Responder rates were calculated based on the proportion of subjects achieving a composite investigator- and subject-assessed improvement of at least 2 grades from baseline scores on the FWS at Day 30. For this endpoint scores were significantly higher for the LCL-treated group (20.3%), and the LCL and GL treated group (21.3%) when compared with placebo (0%). The proportion of responders achieving a score of 0 (none) or 1 (mild) on the FWS for LCL was significantly higher (as rated by both the investigator and the subject) at Day 30 ($p < 0.001$) for the onabotulinumtoxinA group compared with the placebo group. Investigator-assessed responder rates were 59.0% and 54.9% in the onabotulinumtoxinA 44 U and 24 U groups, respectively. Subject responder rates at Day 30 were similar in the onabotulinumtoxinA-treated groups at 48.5% and 45.8%, respectively (Moers-Carpi, 2015). In general, when GL and LCL were treated simultaneously, responder rates were higher than those for LCL treatment alone.

The reported AEs for both Study 1 and Study 2 were mild or moderate in severity, with 58.1% of subjects reporting at least 1 AE. Most AEs were not considered to be treatment-related. The most frequently reported treatment-related AEs included injection site hematoma (including bruises), headache, and injection site hemorrhage, all of which occurred at a frequency of $\leq 3.1\%$ in each of the 4 treatment cycles. Further, the incidence of treatment-related AEs tended to decline with repeated treatment. None of the subjects discontinued treatment due to an AE or SAE (Carruthers, 2015b).

Study 3 was a 5-month, double-blind, randomized, parallel-group, placebo-controlled extension study of the subjects who completed Study 2. Subjects who previously received onabotulinumtoxinA were eligible to receive the same dose in this study, while subjects who previously received placebo were randomized in a double-blind fashion to 1 of 2 treatment arms to receive either onabotulinumtoxinA 44 U or placebo. In this extension study, subjects were eligible to receive up to 2 additional treatment cycles. The endpoints were similar to Study 2 with the primary response being the proportion of subjects achieving a score of 0 or 1 on the FWS at Day 30. A total of 684 subjects were enrolled: 260 to the 44 U onabotulinumtoxinA group, 227 to the onabotulinumtoxinA 24 U, 101 subjects who previously received placebo and were randomized to the onabotulinumtoxinA 44 U group, and 96 subjects who previously received placebo and were randomized to the placebo group. Results were consistent with Study 2 with responder rates significantly higher in the onabotulinumtoxinA-treated groups at Day 30 and at all other timepoints in cycles 3 and 4 when compared with placebo. During the 1-year assessment period, 58.2% of subjects experienced at least 1 AE; however, most were mild in intensity. Notably, the incidence of treatment-related AEs appeared to decline with repeated treatments. Treatment-related AEs, all occurring in $< 3.1\%$ of subjects in each treatment cycle, included site hematoma, headache, and injection site hemorrhage.

As minimally-invasive treatment becomes more widely used and accepted, and both men and women gain increased awareness of the recognition of facial aging and the aesthetic treatment options available, it is important to continue examining the potential benefits of such treatments in the context of unmet clinical need, improved self-satisfaction, and increased demand. Aesthetic products and procedures, while not medically necessary, can significantly improve

social and psychological functioning, as well as self-satisfaction, which can have a meaningful and significant impact on daily life and patient well-being (Fagien, 2008).

[REDACTED]

2.2. Benefit/Risk Assessment

More detailed information about the known and expected benefits and risks and reasonably expected adverse events of DAXI for injection may be found in the Investigator’s Brochure.

	
[REDACTED]
 
[REDACTED]
 
[REDACTED]
 
[REDACTED]
 
[REDACTED][REDACTED][REDACTED][REDACTED] 
[REDACTED]

--	---

4. STUDY DESIGN

4.1. Overall Design

This is a phase 2a, multicenter, open-label, dose-escalation study to evaluate the safety and efficacy of DAXI for injection for the treatment of subjects with moderate or severe LCL. This study will be conducted at 4 sites in the United States.

[REDACTED] Subjects will be screened for eligibility and enrolled into the study after providing informed consent.

Approximately 64 subjects (18-65 years old) with moderate or severe LCL will be enrolled sequentially into 1 of 4 treatment cohorts (approximately 16 subjects per cohort) [REDACTED]. Investigators will make all reasonable efforts to enroll equal proportions of patients with moderate and severe LCL (based on baseline assessments) in each dosing cohort. The total study duration will be up to 38 weeks, including up to 2 weeks for screening. Subjects will be followed for a minimum of 24 weeks and up to 36 weeks or until scores on the maximal expression IGA-LCWS and PLCWS return to baseline (Day 1 Visit), or until Week 36, whichever occurs first. Subjects will then have the Final Evaluation Visit.

Cohorts 1 and 2 will be enrolled simultaneously. Subsequent cohorts (3 and 4) will be enrolled sequentially and gated by the decision from the Data Review Committee (DRC) upon reviewing available data (including safety, efficacy, and photographs/videos) of previous cohorts. The DRC will convene to review data 4 weeks after LCL treatment for the last subject in Cohorts 1 and 2. The DRC will reconvene again after the last subject in Cohort 3 reaches the Week 4 Visit. Revance reserves the right to terminate or stop the study at any time. Refer to Sections 1.2 and 9.5.1 for additional information.

[REDACTED]

[REDACTED]	[REDACTED]	[REDACTED]

[REDACTED]

All treatments will be IM injections administered by the PI. [REDACTED]
[REDACTED]
[REDACTED]
[REDACTED]

The area around the injection sites will be evaluated at the Screening Visit to assess for skin inflammation or active skin disease and at the Day 1, Week 2, and Week 4 Visits to determine if there is a cutaneous reaction to the investigational product. The assessment will be captured as a

global evaluation of the injection sites to assess for erythema, edema, burning or stinging sensation, itching, or bruising.

All subjects will be evaluated for improvement in LCL severity using the Revance-validated 4-point LCWS to assess LCL at rest and at maximum rest by both the investigator (IGA-LCWS) and the subject (PLCWS). An additional investigator- and subject-rated endpoint is the visual assessment of improvement from baseline in LCL severity on the GAIS at each post-treatment visit. Additional subject reported outcomes include responses to the FASE and FACE Q™; Appraisal of Lines: Crow’s Feet Lines questionnaires, as well as the Subject Global Satisfaction with Treatment questionnaire.

[REDACTED]

[REDACTED]

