3.1.1 Determination of Sample Size

The sample size is not determined by the power of formal hypothesis tests.

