3.1.2 Treatments Administered

This is an open-label, non-randomized study for the treatment of moderate or severe LCL. Subjects will be sequentially enrolled by cohort.

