6.5.1 Primary Efficacy Analysis

The proportion of subjects achieving a score of 0 or 1 (none or mild) in LCL severity at maximum smile on the IGA-LCWS at Week 4 after LCL treatment will be summarized. An exact 95% confidence interval for the individual proportions will be provided. A Cochran-Mantel-Haenszel test of association, stratified by baseline IGA-LCWS severity and study center, will be performed. In addition, an exact Cochran-Armitage test for trend, ignoring the stratification factors, will be performed. If the Cochran-Mantel-Haenszel test is significant at the 0.05 significance level, then a linear regression on response will be performed with categorical dose and site as predictors. An unstratified logistic regression analysis may still be used to explore the dose-response relationship.

Additionally, the change from baseline in LCL Severity at Week 4 on the IGA-LCWS at maximum smile will be analyzed using a general linear model with change from baseline as the dependent variable. The model will include baseline severity and study center as fixed categorical effects. The least-square means and standard errors will be presented. Additionally, the differences between dose groups will be presented with corresponding 95% confidence intervals.

[REDACTED]

[REDACTED]

[REDACTED]

[REDACTED]

Statistical Analysis Plan for 1820205

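### The moderate/severe mix is balanced by best effort on an unnamed scale, and no visible responder rate or dose-trend analysis in SAP 6.5.1 adjusts for it, so systematic drift in mix could resemble a dose trend.

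*Protocol*

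**What the plan says.** **Enrolment.** Protocol 4.1 asks for "all reasonable efforts to enroll equal proportions of patients with moderate and severe LCL (based on baseline assessments) in each dosing cohort". No quota or cap is visible there. Protocol 5.1 (items 3 and 4) grades every subject as moderate or severe at maximum smile on both IGA-LCWS and PLCWS. It requires agreement between the two sides of the face, not between the two scales.

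**Allocation.** The study is open-label and non-randomised. SAP 3.1.2 states: "Subjects will be sequentially enrolled by cohort". Protocol 4.1 adds: "Cohorts 1 and 2 will be enrolled simultaneously. Subsequent cohorts (3 and 4) will be enrolled sequentially and gated by the decision" of the Data Review Committee. On size, SAP 3.1.1 says: "The sample size is not determined by the power of formal hypothesis tests".

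**Endpoint.** SAP 2.2.1 defines response as IGA-LCWS 0 or 1 at maximum smile at Week 4.

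**Analyses that ignore severity (SAP 6.5.1).**
- The cohort proportions: "An exact 95% confidence interval for the individual proportions will be provided".
- The exact Cochran-Armitage trend test, which sets the stratification factors aside.
- The linear regression on response that follows a significant CMH test. Its predictors are categorical dose and site.
- The optional logistic regression, described as unstratified.

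**Analyses that use severity.**
- The CMH test in SAP 6.5.1, stratified by baseline IGA-LCWS severity and centre.
- The Week 4 change-from-baseline model in SAP 6.5.1, which includes baseline severity.
- SAP 6.5.4, which says the primary-endpoint regression has baseline IGA-LCWS severity and site as covariates.
- Protocol 9.4.1, which plans logistic regression stratified by baseline LCWS severity and centre.
- SAP 6.2, which tabulates baseline IGA-LCWS and PLCWS by cohort.

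**The concern.** Response is an absolute status, so baseline severity should drive a cohort's rate whatever the dose. Without randomisation, and with Cohorts 3 and 4 enrolled later, the mix can shift in step with dose. The cohort rates and their intervals are what most readers will compare when judging doses, and they carry no adjustment.

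The unnamed scale adds to this. A site could balance on PLCWS, satisfy Protocol 4.1, and still leave the IGA-LCWS strata used in the analysis unbalanced.

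The existing adjusted analyses do not fill the gap. The CMH test gives a p-value but no adjusted rate per dose. The change-from-baseline model gives adjusted means on the severity scale, not responder rates. On whether the response regression adjusts for severity, SAP 6.5.1 says one thing and SAP 6.5.4 and Protocol 9.4.1 say another.

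Protocol 9.4 plans no formal hypothesis tests, so what is at stake is the reading of dose-response, not confirmatory error.

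**Working it through.** **1. The plan's own figure.** 4 cohorts × 16 = 64, as stated. There is no power calculation to reproduce.

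**2. Why mix matters.** From moderate (2), reaching 1 is a drop of 2 − 1 = 1 grade. From severe (3) it is 3 − 1 = 2 grades.

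**3. Crude rates under drift with no dose effect.** The documents give no response rate by severity, so the rates are assumptions: 80% if moderate, 50% if severe. With m moderate subjects of 16, the expected crude rate is [0.80m + 0.50(16 − m)]/16.

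| Moderate of 16, Cohorts 1 to 4 | Crude rates (%) | Gap, Cohort 1 vs 4 | Exact Cochran-Armitage rejects (two-sided 0.05) |
|---|---|---|---|
| 8, 8, 8, 8 | 65.0 in each | 0 | 2.7% |
| 10, 10, 8, 6 | 68.8, 68.8, 65.0, 61.3 | 7.5 points | about 5% |
| 12, 10, 6, 4 | 72.5, 68.8, 61.3, 57.5 | 15 points | about 12% |

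For example, Cohort 1 in the last row is (12 × 0.80 + 4 × 0.50)/16 = 11.6/16 = 72.5%. Reversing the order reverses the sign, so drift can create or hide an apparent trend.

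**4. Range over other assumed rates.** Three more moderate/severe pairs were used, each averaging 57% at 50:50. That is near the 59.0% and 54.9% investigator-rated rates that the Protocol Introduction quotes for another toxin. Severe counts ran 12, 10, 6, 4 of 16, with 40,000 simulated trials per scenario.

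| Moderate / severe | Crude gap | Exact trend test, drift | Exact trend test, 8:8 |
|---|---|---|---|
| 65% / 49% | 8 points | 5.9% | 3.6% |
| 72% / 42% | 15 points | 12.3% | 2.9% |
| 80% / 34% | 23 points | 24.2% | 1.9% |

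With severe counts 10, 10, 8, 6 the gaps were 4, 7.5 and 11.5 points, and rejection was 4.2%, 5.0% and 6.4%.

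**5. Do adjusted analyses repair it?** In the simulations of step 4, a CMH test stratified by severity rejected in 4.5% to 4.8% of drift trials. At the larger drift a severity-stratified trend test rejected in 4.7% to 4.8%, and rates standardised to 50:50 averaged 57% in every cohort. Centre was not simulated. With it, 4 sites × 2 severities = 8 strata, averaging 16/8 = 2 subjects per cohort per stratum.

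**6. Chance imbalance versus drift.** The Introduction reports, for an earlier trial of another toxin: "At baseline, 60.5% of subjects had severe LCL". If each subject were severe with probability 0.605, the response rate would be 0.395 × 0.80 + 0.605 × 0.50 = 0.6185, with variance 0.6185 × 0.3815 = 0.2360 per subject. That splits into 0.2145 within severities and 0.605 × 0.395 × 0.30² = 0.0215 between them. The binomial SE, √(0.2360/16) = 12.1 points, therefore already includes the √(0.0215/16) = 3.7 points due to a chance mix. Only systematic drift lies outside the exact interval.

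**7. Price of standardising.** The estimate is ½p(moderate) + ½p(severe). At 12 moderate and 4 severe its SE is ½√(0.16/12 + 0.25/4) = 13.8 points. The crude SE is √(12 × 0.16 + 4 × 0.25)/16 = 10.7 points.

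**The case against.** The strongest reply is that severity is already handled. The CMH test is stratified on it and holds its level in the check above. The change-from-baseline model gives severity-adjusted dose differences with intervals. Protocol 9.4.1 and SAP 6.5.4 call for adjustment, and SAP 6.2 would show a drifting mix. SAP 6.5 also withholds between-cohort differences unless the table shells call for them. All of this stands. A reader might infer that the whole primary analysis is confounded by severity, and the documents do not support that. The problem is confined to the crude rates, the unstratified trend test and the two unadjusted regressions.

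The larger drift is also severe. It reverses a 3:1 mix to 1:3 despite an instruction to aim for equality, and Cohorts 1 and 2 enrol together, so the passage of time does not explain 12 versus 10. At the milder drift the exact test stays at roughly its nominal level. For scale, the exact 95% interval for 9/16 runs from 0.30 to 0.80, so even a 23-point gap sits within one cohort's uncertainty.

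A reader might also infer that ordinary chance imbalance invalidates the exact intervals (step 6 shows it does not), or that a hard cap per severity is required. A cap is a debatable trade-off. Cohort 4 has no later cohort to take deferred subjects. Subjects deferred to a gated cohort would face a review held at least 4 weeks after the last treatment, against a 14-day screening window, and so would need rescreening.

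Finally, text beside the balancing sentence and after SAP 6.5.1 and 6.5.4 is redacted. The statements on the unnamed scale and missing adjusted rates apply to the visible text only.

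**Conclusion.** The point holds in limited form. The balancing scale is unnamed, no severity-adjusted responder rate per cohort is visible, and SAP 6.5.1 conflicts with SAP 6.5.4 and Protocol 9.4.1 on whether the response regression includes severity. Large systematic drift with no dose effect gives a spurious gap of 8 to 23 points in the crude rates and rejection by the exact trend test in about 6% to 24% of trials. Mild drift gives gaps of 4 to 11.5 points and rejection of about 4% to 6%, little or no excess. These sizes rest on assumed rates by severity and assumed drift patterns. Nothing in the documents shows that drift will occur. The change is worth making because it uses data already collected and costs little.

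**What to change.** 1. **Protocol 4.1.** State that the balance of moderate and severe subjects is judged on the pre-treatment IGA-LCWS at maximum smile, which matches the CMH strata. Keep best-effort enrolment, without a cap.
2. **SAP 6.5.1, display.** Beside each crude proportion, report the responder rate by baseline IGA-LCWS severity and the rate standardised to a 50:50 mix with a 95% CI. Name the interval method, since a stratum may hold only about 4 subjects, and say what is shown if a stratum is empty. Use the same population-count denominators as SAP 6.5.
3. **SAP 6.5.1, dose-response.** Include baseline IGA-LCWS severity in the regression, and add a severity-stratified trend test beside the Cochran-Armitage test. Reconcile the regression's form and covariates with SAP 6.5.4 and Protocol 9.4.1.

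**Cost.** One clarified sentence, a few table columns and one more test. The standardised rate is less precise when a stratum is small (SE 13.8 against 10.7 points at 12:4), so it should sit beside the crude rate and not replace it. No extra subjects or assessments are needed.

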4.4. Visit Schedule

A Screening Visit will be conducted up to 2 weeks prior to enrollment, and subjects will receive investigational product at baseline (Day 1). Following treatment, subjects will complete a paper diary for 2 weeks to capture their assessment of improvement in the appearance of LCL. A follow-up safety phone call will be conducted at Week 1. Post-treatment on-site follow-up visits

will occur at Weeks 2, 4, 8, 12, 16, 20, 24, 28, 32, and 36. The total study duration will be up to 38 weeks, including up to a 2-week screening period. Subjects will be followed for a minimum of 24 weeks post-treatment and up to 36 weeks or until scores return to baseline for the maximal expression IGA-LCWS and PLCWS or until the Week 36 Visit, whichever occurs first. Subjects will then have a Final Evaluation Visit.

Subjects will be evaluated for LCL severity using the Revance-validated 4-point IGA-LCWS and PLCWS at rest and at maximum smile effort.

5. STUDY POPULATION

Approximately 64 female or male subjects, 18-65 years old, with moderate to severe LCL will be enrolled. Subjects must meet all of the inclusion criteria and none of the exclusion criteria to be eligible for the study

5.1. Inclusion Criteria

To be eligible for participation, subjects must:

1. Provide written informed consent consistent with International Conference on Harmonisation (ICH)-Good Clinical Practice (GCP) guidelines and local laws, including authorization to release health information, signed prior to any study procedures being performed
2. Be outpatient, male or female subjects, in good general health, 18-65 years old
3. Have a score of moderate (2) or severe (3) LCL at maximum smile effort as assessed by the IGA-LCWS (scores must be consistent bilaterally)
4. Have a score of moderate (2) or severe (3) LCL at maximum smile effort as assessed by the PLCWS (scores must be consistent bilaterally)
5. Have sufficient visual acuity without the use of eyeglasses (contact lens use is acceptable) to accurately assess their facial wrinkles
6. Be willing to refrain from receiving facial fillers, laser treatments, use of any product that affects skin remodeling, or a product that may cause an active dermal response in the treatment areas (e.g., above the oral commissures) from screening through the end of the study
7. All women of childbearing potential (WOCBP) must have a negative urine pregnancy test (UPT) result at the Screening and Baseline Visits and must practice an effective method of contraception throughout the study (e.g., oral contraceptive pill, injection, implant, patch, vaginal ring, intrauterine coil, intrauterine device, tubal ligation, barrier method) used WITH an additional form of contraception (e.g., sponge, spermicide or condom); abstinence; no heterosexual intercourse; or has a vasectomized partner (refer to Section 5.6 for additional information)
8. Able to understand the requirements of the study and be willing and able to follow all study procedures, attend all scheduled visits, and successfully complete the study.

